Appendix A. Schedule of Measurements

	BL (pre-op)	Op	6 wks (post- op)	3m	6m	12m	18m	24m [†]
MESA	✓*			✓	✓	✓	✓	✓
H+P	✓**							
POP-Q	✓*				✓	✓		✓
Stress Test	✓				✓	✓		✓
PVR	✓				✓	✓		✓
Q-Tip	✓					✓		✓
UDS	✓							✓
Voiding Diary	✓*				✓	✓		✓
Pad Test	✓*				✓	✓		✓
Med. Audit	✓*			✓	✓	✓	✓	✓
Expectations of Surgery	✓*							
Resumption of Activities	✓			✓	✓			
QOL	✓*			✓	✓	✓	✓	✓
Sexual Function	✓*				✓	✓	✓	✓
Operative Measures		✓						
Satisfaction with Surgical Results				✓	✓	✓	✓	✓
Complications		✓	✓	✓	✓	✓	✓	✓
Pain ← surgery			✓	✓	✓	✓	✓	✓
Incomplete Bladder Emptying			✓					
Readmission			✓	✓	✓	✓	✓	✓
New Interventions or Re-treatment			✓	✓	✓	✓	✓	✓

* Must be completed < 6 months prior to randomization. If surgery is delayed, these may have to be reassessed.

** Eligibility sections of History & Physical must be < 6 months prior to randomization. If surgery is delayed, these may have to be reassessed.

† Or at time of treatment failure, if earlier. If patient is surgically retreated and therefore has UDS prior to 24-months as part of the treatment failure battery, UDS are not done again at 24-months.

Appendix B. Complications of Surgery

A. Serious complications that mandate report to the DSMB within 72 hours:

1. Acute serious morbidity and mortality related to surgery: death; myocardial infarction; cerebrovascular accident; pulmonary embolus; renal failure; sepsis requiring admission to ICU; major anesthetic misadventure requiring admission to ICU.
2. Complications which contribute to serious morbidity on a subacute or chronic basis: abscess or infected hematoma that requires open or percutaneous intervention; injury to adjacent organ (injury to bladder, bowel, ureters, or vascular structures) which requires open, percutaneous, or endoscopic operations; fistula; nerve injury (specify site); deep venous thrombosis.

B. Complications of moderate or minor concern that are reportable to the DSMB at set intervals:

1. Complications which are of moderate concern and contribute to morbidity on a chronic basis: sling erosion; hernia; need for transfusion.
2. Short-term complications or minor complications: wound separation; hematoma, or seroma NOT specified above; atelectasis; pneumonia; cystitis or pyelonephritis (any antibiotics given for urinary tract symptoms); anesthetic minor complication (including aspiration pneumonia, laryngospasm, infection at catheter site); bladder injury.

C. Site-specific complications or deviations:

The DSMB must consider these complications in the light of individual surgeons and sites, including procedure-specific differences in primary outcome (cure of incontinence) and important but less serious complications (need for take-down.) A single surgeon or site that deviates significantly from the rest of the network should be evaluated for proficiency in that procedure, and consideration given to exclusion of data from that surgeon and/or site from final analyses.

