*Patient can be deferred for enrollment until respective time interval has been met.

E.2 Exclusion Criteria

1. Age < 21 years
2. Non-ambulatory (Ambulatory with assistive devices does not exclude the patient.)
3. Pregnancy by self-report or positive pregnancy test, or self-reported intention to become pregnant in the next 24-months
4. Current cancer chemotherapy or radiation therapy
5. Systemic disease known to affect bladder function (i.e., Parkinson's disease, multiple sclerosis, spina bifida, spinal cord injury or trauma)
6. Urethral diverticulum, current or previous (i.e. repaired)
7. Prior augmentation cystoplasty or artificial sphincter
8. < 12 months post-partum*[†]

9. Recent pelvic surgery (e.g. vaginal hysterectomy), i.e., endoscopic pelvic surgery <6 weeks or open pelvic surgery <6 months*
10. Participation in another treatment intervention trial that might influence the results of this trial.

*Patient can be deferred for enrollment until respective time interval has been met.

†“Partum” is defined as a delivery or other termination that occurs after 20 weeks.

If more than 6-months transpires between determination of eligibility and surgery, specified measures must be repeated to ensure current eligibility for the trial as well as to obtain current baseline values for critical measures that are subject to change. (See Section H.5 and Appendix A.)

F. RANDOMIZATION

Patients will be randomized in the operating room. It is recognized that there are disadvantages to this strategy, including the following points:

- Patients must agree to be blinded to the type of surgery they will get until after the operation;
- The surgeon(s) must be prepared to perform either type of procedure;
- The anesthesiologist must be willing and able to evaluate the patient without knowing which procedure will be performed.

The process of obtaining the randomized treatment assignment will be accomplished via a telephone call to an automated randomization system at the Biostatistical Coordinating Center (New England Research Institutes) from a touchtone telephone. A back-up hard copy of the assignment kept in a sealed envelope will be made available in the case of technical problems. Randomization will be stratified by clinical site, using permuted blocks.

G. TREATMENTS

G.1 Operative Procedures

The two procedures included in this trial are the Burch modified Tanagho procedure and the autologous fascia sling procedure.

G.2 Standardization of Operative Procedures

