Adverse events, defined as “unanticipated problems,” have been specified for this trial. The list of reportable AEs was approved by the DSMB and is provided in Appendix B and at the bottom of the Adverse Event Form. There are two categories of AEs: 1) Serious Adverse Events and 2) Adverse Events. Serious adverse events are required to be reported to the BCC and NIDDK within 72 hours of occurrence or knowledge of the event. Adverse events not in the “serious” category, but judged to be “severe” or “life threatening” are also subject to the 72 hour reporting requirement. This reporting requirement is met by completing an Adverse Event Form and faxing it to the BCC and NIDDK. Copies of reports of all SAEs will be forwarded to the Chairperson of the DSMB.

At the bi-annual meetings of the DSMB, summary reports of all reportable AEs will be reviewed. The BCC is responsible for preparing these summary reports. Interim monitoring by the DSMB is also discussed in Section K2. After review, the Executive Secretary of the UITN DSMB is responsible for generating a brief summary report for distribution to all clinical sites, the BCC, and NIDDK. The report will document that a review of data and outcomes across all centers took place on a given date. It will also inform Investigators of the DSMB’s conclusion with respect to progress or need for modification of the protocol. Investigators are required to submit a copy of this report to their local IRB. If there is any correspondence with the DSMB outside of the planned meetings that has study-wide implications, it is the responsibility of the Executive Secretary of the UITN DSMB to draft an appropriate memo for distribution to all clinical sites, the BCC, and NIDDK. Again, Investigators are responsible for submitting a copy of this correspondence to their IRB.

K. STATISTICAL CONSIDERATIONS

K.1 Sample Size Determination for Primary Endpoints

Two primary endpoints will be used: 1) “overall treatment success” to evaluate a broadly defined pragmatic benefit of surgery and 2) “treatment success specific to SUI” to evaluate a more narrow and mechanistic measure of benefit. See Section D for criteria. The primary time point for evaluating success is at 24-months. Although these measures of success cannot be fully documented until 24-months, a failure can be documented earlier (if, for example, a patient requires surgical treatment or has a positive stress test at 12-months).

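### Appendix B A.1 makes death and other major events reportable only when acute and related to surgery, without defining either term, so DSMB reporting of events judged unrelated is not assured

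*Protocol*

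**What the plan says.** Protocol Section J sets up adverse event reporting by reference to a list: "The list of reportable AEs was approved by the DSMB and is provided in Appendix B". It adds that the same list is printed on the Adverse Event Form.

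In Appendix B, part A is headed "Serious complications that mandate report to the DSMB within 72 hours". Its first item is "Acute serious morbidity and mortality related to surgery: death; myocardial infarction; cerebrovascular accident; pulmonary embolus; renal failure", followed by sepsis and anesthetic misadventure that need intensive care. Item A.2 covers subacute and chronic complications, and part B covers moderate and minor ones.

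Section J also fixes the route: "Serious adverse events are required to be reported to the BCC and NIDDK within 72 hours of occurrence or knowledge of the event". Events outside the serious category but judged severe or life threatening "are also subject to the 72 hour reporting requirement". For the DSMB it says "Copies of reports of all SAEs will be forwarded to the Chairperson of the DSMB", and "At the bi-annual meetings of the DSMB, summary reports of all reportable AEs will be reviewed".

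On blinding, Section F says only "Patients must agree to be blinded to the type of surgery they will get until after the operation".

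**The concern.** A.1 puts two conditions, acute and related to surgery, on the gravest events in the trial and defines neither. The 72 hours is a deadline for sending the report. It does not say when an event must occur in order to count. Follow-up runs to 24 months, so there is ample room for events whose relation to the operation is a matter of opinion.

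Two things are at stake. The first is oversight: the DSMB should be certain of seeing every death, by arm, whatever anyone thinks caused it. The second is the comparison itself. Complications are a secondary aim (Section A), and Section K.3 compares complication rates with Fisher's exact test. Randomization protects a comparison of all events in a fixed period. If events enter the count only after someone who knows the procedure has called them related, that protection is lost for those events.

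**Working it through.** No figure in the protocol bears on this point, so there is nothing to recompute. The check is to follow two events through every reporting route: a death in the second year, and a pulmonary embolus some weeks after surgery, each judged unrelated to the operation.

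1. **The list (Appendix B).** Death and pulmonary embolus stand only under A.1. Neither event, as judged, is related to surgery, and the death is hardly acute in relation to the operation. On a plain reading neither meets an entry. By contrast, deep venous thrombosis (A.2) and pneumonia (part B) are listed without an express causal condition in their item headings.

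2. **Copies of SAE reports (Section J).** All SAE reports go to the DSMB chair. This forwards what has been classed as an SAE. Section J says the adverse events for this trial have been specified and points to Appendix B, so the route appears to inherit the A.1 conditions.

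3. **The severity route (Section J).** The extra 72-hour rule has no relatedness condition, but it applies to adverse events in the non-serious category. It does not clearly reach an event that is not on the list.

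4. **Summaries at the twice-yearly meetings (Section J).** These cover reportable events, which is the same list again.

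5. **DSMB reports (Section K.2).** These will ordinarily summarize adverse events and unanticipated problems, with no relatedness condition. This route could carry both events. It describes usual content, however, and does not require deaths to be itemized.

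6. **Data capture.** Appendix A schedules complications and readmissions at every contact from 6 weeks to 24 months. Appendix C records reasons for readmissions and emergency admissions through 3 months. Section N tracks censoring and loss to follow-up. An embolus that led to readmission would be in the database, and a death should show as censoring. No sentence requires either to be passed to the DSMB from there.

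**Who judges.** No section names an assessor of relatedness. The surgeon necessarily knows the procedure, and the only blinding described is the patient's, which ends after the operation. It is therefore plausible, though not stated, that the judgement falls to staff who know the arm. Appendix B part C has the DSMB consider complications by surgeon and site, with possible exclusion of a deviating surgeon's or site's data, so the person judging may not be indifferent to the answer.

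**Result.** Routes 1, 2 and 4 depend on the list, and route 3 is unclear. Routes 5 and 6 may reveal the events but impose no duty to report them. The recipients also differ: Appendix B names the DSMB for the 72-hour report, while Section J names the BCC and NIDDK and has copies forwarded to the DSMB chair.

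**The case against.** The strongest reply is that *related to surgery* in A.1 is a category label, parallel to the subacute or chronic label in A.2, and not a causal test. The appendix is titled as a list of surgical complications, so some link to surgery is implied for every entry and A.1 is not alone in that. This stands as far as it goes: it would be wrong to say that A.2 and part B are free of any such link. But A.1 is the only item that states the condition outright, and it does so for death.

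A reader might infer that deaths judged unrelated never reach the DSMB. The protocol does not support that. Section K.2 is not limited to related events, and readmission and loss-to-follow-up data would show some of them. What is missing is an assurance that they will be reported.

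A reader might also infer that the unblinded site decides. That is an inference, since no section assigns the judgement. The Manual of Operations is cited but not shown and may define the terms and the assessor; the Adverse Event Form is not shown either, although Section J describes it as carrying the same list.

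Finally, the DSMB approved the list, and both operations are described in Section K.2 as standard with well-known complications. This makes a large hidden safety signal less likely. It does not make the wording clear.

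**Conclusion.** The point holds as a defect of wording with a cheap remedy. A.1 conditions the reporting of death, myocardial infarction, cerebrovascular accident and pulmonary embolus on two undefined terms, with no event window and no named assessor. Because Section J makes Appendix B the reportable list, reporting to the DSMB of such events when they are judged unrelated is not assured. The comparison of serious complications could also depend on that judgement.

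The size cannot be given. The protocol states no mortality, no rate of A.1 events and no likely split in attribution between the arms, and any figure would rest wholly on assumed rates. The conclusion rests on reading A.1 literally and on Section J's list being the operative definition. If the Manual of Operations already requires all deaths to be reported, the remaining task is to bring the protocol into line with it.

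This should be changed, because it concerns the most serious outcomes and the visits needed to collect the data already exist. It does not threaten the primary analysis.

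**What to change.** Change Appendix B A.1 and bring the related text into line:

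- List death from any cause during follow-up as reportable.
- List the other A.1 events as reportable regardless of judged relation to surgery within a fixed post-operative window tied to an existing visit. The 6-week visit is one example; the window is the sponsor's choice.
- Remove *acute* or define it. If non-fatal events after the window stay conditional on relatedness, define that term and name the assessor, since the filter remains for those events.
- Record relatedness as a separate field on the Adverse Event Form, so that it describes an event and does not decide whether it is reported.
- Base the comparison of A.1 events between arms on all events in the window.
- Reconcile A.1 with Section J (recipients and what counts as an SAE) and with Section K.2, so that DSMB reports always include all deaths by arm.

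The cost is wording in Appendix B and the two sections, and one form field. The downside is that a few events unrelated to surgery will be reported.

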First, we expect very little primary endpoint data to be available while any participants are still at risk for exposure to either surgery being evaluated. Accrual is expected to take 24-months and success on the primary endpoints is not documented until 24-months after surgery. Therefore, at the time the first participants are reaching the assessment time for documenting “success”, all or nearly all patients will already have had their surgery. Nevertheless, there will be some information on the primary endpoints prior to 24-months, since self-reported stress-type symptoms, a positive diary, positive pad test or positive stress test at 6-24 months, or retreatment for SUI at any time prior to 24-months will be considered a failure.

Second, both the Burch modified Tanagho and the autologous fascia sling procedures are “standard” surgical procedures. Unlike a trial evaluating a new surgical procedure, the study procedures in this trial have generally well-known complications. It is unlikely that we will experience any new or unexpected complications. Of course, we will collect and document complications but we do not expect that treatment group differences in surgical complication rates would pose an ethical imperative to stop the trial, unless some serious unexpected complication is prevalent. Rates of the more serious surgical complications (e.g. organ damage, sling erosion, hernia, wound infection) will be summarized separately within each site and further within each surgeon, to monitor for problems with specific hospitals or surgeons.

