Appendix C. Perioperative Measures

Preoperative Measures

- Adjuvant behavioral or biofeedback in previous 30 days: type and # sessions

Operative Measures

For both procedures:

- Date of surgery
- Surgery performed (1. Burch, 2. sling)
- More than one surgery; specify (List: enterocele repair, colpopexy, cystocele and rectocele repair, vaginal or abdominal hysterectomy, hernia repair; paravaginal repair; other)
- Assistant: Resident, Fellow, non-study surgeon – level and specialty
- Operative time: enter OR, start incision, wound closed, leave OR
- Type of anesthesia (LIST: 1. General, 2. Spinal, 3. Epidural, 4. Sedation, 5. Local, 6. None)
- Estimated blood loss: ____ ml as recorded by anesthesiologist
- Blood transfusion: #units, autologous (Yes, No)
- Suture material and gauge
- Intraoperative complications (e.g., urethral or bowel injury) [see Appendix B]
- Urine drainage: SP tube, urethral catheter, no catheter
- Cystoscopy: abnormal findings; describe intraoperative and corrected complications
- Was randomization violated, i.e., any deviation from randomized procedure

For Burch procedures

- Suture material and gauge
- Number sutures on each side
- Length of abdominal incision
- Orientation of incision: vertical, horizontal, other
- One vs. two passes through Cooper's ligament

For sling procedures

- Sling material: autologous fascia (rectus; if fascia lata, specify reason)
- Size of sling material: ____ cm long x ____ cm wide
- Suture of sling material: simple one stitch, two stitches, helical x3, other
- Abdominal incision
 - Length of incision
 - Orientation of incision: vertical, horizontal, other
- Device to pass suture/sling from vagina to site of anchoring: specify device [LIST: Stamey needle, commercial device. If commercial device, specify name of device and brand.
- Folding of sling ends: Yes/No
- Tied suture over/to rectus fascia

Post-Operative Measures

- Complication(s): specify (see Appendix B)
 - In recovery room
 - First 24-hours after leaving recovery room
- Fever > 101°F, 38.3°C during hospitalization: specify
- Blood transfusion during hospitalization: # units, autologous (Yes, No)
- Length of hospitalization
- Audit of discharge medications
- Voiding at discharge
- Estimated residual urine volume
- Discharge with catheter: SP tube, urethral, clean self cath, none
- Pain

Perioperative Measures through 3 months

- Physician visits: number, reason
- Complications: specify
- Readmissions: date, reason, LOS for each

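### Appendix B lists bladder injury as both serious and minor, so an injury repaired during the index operation falls under two reporting rules

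*Protocol*

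**What the plan says.** Appendix B of the protocol has two graded lists.

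- List A is headed "Serious complications that mandate report to the DSMB within 72 hours". Its item A.2 opens with "Complications which contribute to serious morbidity on a subacute or chronic basis" and then names, among others, "injury to adjacent organ (injury to bladder, bowel, ureters, or vascular structures) which requires open, percutaneous, or endoscopic operations".
- List B is headed "Complications of moderate or minor concern that are reportable to the DSMB at set intervals". Its item B.2, for short-term or minor events, ends with "anesthetic minor complication (including aspiration pneumonia, laryngospasm, infection at catheter site); bladder injury". Nothing limits the bladder entry. Another entry in the same item is limited: "hematoma, or seroma NOT specified above".

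Section J makes the lists operational. They are reproduced on the Adverse Event Form, and a serious event must reach the coordinating center and the NIDDK within 72 hours. Section J also expedites a non-serious event that is judged severe or life threatening.

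Appendix C expects problems to be found and dealt with during surgery. Its cystoscopy item asks the team to "describe intraoperative and corrected complications". It also refers intraoperative complications, with bowel injury as one example, to Appendix B. Section G.2 requires cystoscopy in both arms, and section G.4 rules out laparoscopic versions of both procedures.

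**The concern.** A bladder injury that is seen and repaired before the index operation ends was repaired through an open incision or through the cystoscope. On its wording A.2 can cover it, and B.2 covers every bladder injury. The protocol names no tie-break and no adjudicator. One site could send a 72-hour report for the same event that another site leaves to the periodic summary.

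Two things are at stake. The first is the reporting deadline. The second is any count of serious complications. Complications are a secondary aim. Section K.2 plans summaries by site and by surgeon for "Rates of the more serious surgical complications (e.g. organ damage, sling erosion, hernia, wound infection" and similar events. Part C of Appendix B asks the DSMB to look at surgeons or sites that stand apart from the network. A count built on the A/B grade would partly reflect how each site reads the list.

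**Working it through.** The point rests on no stated sample size, power or alpha, so there is no figure of the plan to reproduce. The check is a comparison of the entries, case by case.

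| Case | A.2 (serious) | B.2 (minor) | Settled? |
|---|---|---|---|
| Bladder injury, no operation needed | Does not apply | Applies | Yes, minor |
| Bladder injury, separate later operation | Applies | Applies literally, but A.2 is the specific entry | Yes in practice, serious |
| Bladder injury, repaired within the index operation | Applies if that repair counts as a required operation | Applies | No |
| Bowel, ureteral or vascular injury, repaired within the index operation | Applies if that repair counts | No entry | No |

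A.2 can be read in two ways.

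1. *Repair within the index operation counts.* The bladder injury in row 3 is then in both lists, with two deadlines.
2. *Repair within the index operation does not count.* The bladder injury is then only in B.2. The injury in row 4 falls out of Appendix B altogether, because list B names no organ injury other than bladder. Yet Appendix C sends intraoperative bowel injury to Appendix B to be classified.

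The first reading leaves a conflict and the second leaves a gap, so neither makes the appendix consistent. The drafters did make one B.2 item exclusive of what stood above it (hematoma or seroma), but not the bladder item.

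**Size.** The protocol gives no bladder injury rate. As an assumption, take 1%, 3% or 5% of women with a bladder injury, all repaired at the index operation. The target is 650 women in total (section K.1) and 73 per center (section L).

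- Whole trial: 650 × 0.01 = 6.5; 650 × 0.03 = 19.5; 650 × 0.05 = 32.5 events without a settled category.
- One center: 73 × 0.01 = 0.7; 73 × 0.03 = 2.2; 73 × 0.05 = 3.7 events.

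Two centers with the same experience could therefore differ by about 1 to 4 serious events purely through reading the list differently.

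**The case against.** The strongest reply is that the opening words of the two items already sort the case. A.2 speaks of serious morbidity that is subacute or chronic, and B.2 of short-term or minor events, so an uneventful repair during surgery already under way belongs in B.2. This has weight, and the opening words do lean that way. They are descriptive headings, however, not a stated rule, and this reading leaves bowel, ureteral and vascular injuries repaired at surgery without a category.

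A second reply is that little is lost. All reportable events reach the DSMB at its regular meetings, severe ones are expedited in any case, and Appendix C already records corrected intraoperative problems and later abdominal or pelvic surgery. This stands in part: the underlying facts will often be recoverable. It does not settle which deadline applies. Section O also mentions instruction manuals for the forms. They are not at hand and may say more.

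A reader might go further in three ways that the protocol does not support.

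- *That the operating surgeon chooses the grade knowing the arm, and so biases the arm comparison.* No section says who assigns the category, and section K.3 speaks only of complication rates, without reference to lists A and B. Randomization is stratified by site, so different site readings should fall about equally on both arms. Bias between arms would need grading that differs by arm within sites.
- *That section K.2 sets up a competing severity scale because it names sling erosion and hernia.* Its list is a set of examples and does not refer to the Appendix B categories.
- *That coding differences could remove a site from the final analyses.* Part C of Appendix B refers to the complications as a whole and to outcome, and does not tie that step to the serious list.

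**Conclusion.** The double listing is real and gives one foreseeable kind of event two reporting rules. It is confined to organ injuries repaired during the index operation: a conflict for bladder, and an unstated rule for bowel, ureter and vessels. Bladder injuries that need a separate later operation, or no operation, can be classified.

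The certain consequence is an undefined reporting deadline. The conditional one is that any tally using the serious grade, including one compared across sites and surgeons, depends on how each site reads the list. Its size cannot be taken from the protocol; the 7 to 33 events trial-wide rest on the assumed 1% to 5% and on all repairs being made at the index operation. The definitions of the two primary endpoints in section D do not use the complication grade and are unaffected. No distortion of the comparison between arms is shown.

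**What to change.** - In B.2, limit the entry to bladder injury not specified in A.2, as that item already does for hematoma and seroma.
- In A.2, state whether a repair made within the index operation counts as a required operation, and apply the same rule to bowel, ureteral and vascular injuries. If it does not count, say where those injuries belong. The sponsor decides which grade applies; the request is only that the passages be reconciled.
- On the Adverse Event Form, record for each organ injury whether it was repaired at the index operation or needed a separate one.
- Report any bladder injury by arm regardless of grade, so that this comparison does not depend on the classification.

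The cost is a few words in Appendix B, one form item and possibly a few more 72-hour reports. Sample size and the primary analysis do not change.
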